4.1 Description of study design

This is a national, multi-center, open-label, phase IIIb trial to determine the efficacy and safety of treatment with ribociclib (LEE011) plus letrozole in patients with HR+, HER2-negative advanced (recurrent or metastatic) breast cancer.

In this trial a total of 500 patients from approx. 100 centers will be recruited.

Figure 4-1 Study design

The study is sub-divided in the following periods:

Once the Patient Informed Consent Form has been signed and eligibility is confirmed (all inclusion/exclusion criteria have been verified), the patient can be enrolled. All screening evaluations should be performed within 21 days prior to treatment Day 1.

Patients will be treated with daily doses of 600 mg ribociclib (3-weeks-on/1-week-off schedule) in combination with 2.5 mg letrozole daily (continuous dosing). Dose adjustments (dose reduction or interruption) according to safety findings will be allowed. During the study, visits will be performed at baseline, cycle 1 on day 1 & 15 and cycles 2-EOT on day 1. Study treatment will continue until progression, unacceptable toxicity, withdrawal of consent or 80 weeks after the last patient has been enrolled in the trial, whichever comes first.

Novartis will provide ribociclib and letrozole (and goserelin for premenopausal patients) for all patients who are enrolled prior to commercial availability of ribociclib. For patients enrolled afterwards within the approved indication according to SmPC, the investigator will prescribe both ribociclib and letrozole after evaluation of the individual medical patient need for the treatment with ribociclib and letrozole. Patients who are enrolled outside of the label according to SmPC will be provided with study drug by Novartis (i.e. patients in cohort B).

Further treatment after progression will be at the investigator's discretion. Tumor evaluations through CT will be performed for Screening and every 12 weeks during the

study as well as for End of treatment, in case progression as measured by CT was not the reason for end of the treatment.

Patients will be followed up for safety for 30 days after the last dose of study drug. AEs/SAEs with a suspected causality to the study drug must be reported beyond this 30 days safety interval.

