2.1 Data analysis general information

The data were analyzed by [REDACTED]. Analysis was carried out using the SAS (Statistial Analysis System) software, version 9.2, 2009, SAS Institute Inc., Cary, North Carolina, USA.

Interim analyses were carried out by [REDACTED] as well. The analyses were based on definitions within this SAP and RAP 7.1 and the tables generated for the particular interim analyses were marked in RAP 7.2.

The first interim analysis included a preliminary analysis of safety (as well as baseline characteristics). The second interim analysis included a preliminary analysis of safety, efficacy and quality of life. The third interim analysis included a preliminary analysis of safety and efficacy. The primary efficacy and safety analysis was conducted on all patient data at the time all patients who are still receiving study drug had completed at least 24 weeks of treatment (or discontinued prematurely). The additional data for any patients continuing to receive study drug past these times, as allowed by the protocol, were further summarized in a report once these patients completed the study.

In general, categorical variables were summarized by absolute and relative frequencies. Continuous variables were summarized by descriptive statistics (number of non-missing observations, mean, standard deviation, minimum, median and maximum). Time-to-event data including rates of affected patients were assessed using the Kaplan-Meier method. The primary aim of this trial was in estimation rather than significance testing of statistical hypotheses. Thus, mainly statistical estimators along with appropriate two-sided 95% confidence intervals were used. However, changes from baseline were explored using suitable statistical tests for paired samples. No adjustment for multiplicity was done due to the exploratory nature of the trial.

The data from all participating centers were combined, so that an adequate number of patients was available for analysis and the factor center was included in the analysis of the primary endpoint.

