2.4 Treatments (study treatment, rescue medication, concomitant therapies, compliance)

2.4.1 Study treatment / compliance

Duration (days) of study treatment exposure for patients who took at least one dose of any of the components of the study treatment was calculated as the difference between the last and first day of drug application +1 day. For details see 5.2.1.

The duration includes the periods of temporary interruptions for any reason. Additionally, duration of drug exposure was summarized using descriptive statistics separately for ribociclib, letrozole and goserelin, respectively.

The cumulative dose, dose intensity (DI) and relative dose intensity (RDI) were summarized by cohort. Cumulative dose is defined as the total dose given during the study treatment exposure. For patients who did not receive the respective drug the cumulative dose was set to zero (in case of goselerin for pre- and perimenopausal patients only). The dose intensity (DI) for patients with non-zero duration of exposure is defined as cumulative dose / duration of exposure. For patients who did not receive any drug, the DI was set to zero. Planned dose intensity (PDI) is the assigned dose in mg/day prescribed by the investigator to be given to patients. Relative dose intensity (RDI) is defined as DI divided by PDI. The DI and RDI were summarized separately for each of the study treatment components, but using the duration of the whole study treatment exposure, not the duration of each of the components. In addition, for combinations, the RDI was calculated as mean RDI of each of the study treatment components on a per-patient basis.

Ribociclib interruptions (defined as null doses for any reason except “as per protocol”) were displayed by the number of affected patients, the total duration and frequencies of study drug interruptions. The total duration was calculated by end date – start date of interruption (for any reason except “as per-protocol”) + 1 day. All interruptions of a patient are summed up to the total duration (for any reason except “as per protocol”)

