2.8.1 Adverse events (AEs)

Summary tables for adverse events (AEs) include only AEs that started or worsened during the on-treatment period plus 30 days, the **treatment-emergent** AEs. However, all safety data (including those from the pre and post-treatment periods) will be listed in CSR section 16.2. Absolute and relative frequencies for patients with AEs collected during the pre-treatment and post-treatment period are presented.

The following analyses are presented for the different types of AEs:

	Incidence (frequency table)	Two-level frequency table SOC x PT (MedDRA)	Patient data Listing (section 14.3.1)	Maximum severity (frequency table)	Time to event	Dur- ation of event	Recurrence/ frequency of events per patient
Treatment emergent AEs	X	X		X			
Treatment emergent serious AEs	X	X	X	X	X	X	X
Treatment emergent non-serious AEs	X	X					
TEAE with suspected drug relation to ribociclib	X	X					
TEAE leading to permanent discontinuation of study drug	X	X					
TEAE of special interest	X	x	x		X	X	X
Death (in pre-/on-/post-treatment period)	X		X				

The **incidence frequency table** presents the number, percentage and 95% confidence for occurrence of at least one event of the respective AE type. This table is separated by each of the observation period (pre-/on-/post-treatment) and total. Denominator (for each period) is the number of patients in the Safety Analysis Set (SAF).

The **two-level frequency table** calculates absolute and relative frequencies for MedDRA System Organ Classes (SOC) and Preferred Terms (PT) within SOCs. Again, the number of patients in SAF is used as denominator and each event is counted only once in the respective category. The MedDRA version currently available at time point of analysis is used for decoding.

The **frequency table for maximum severity** analyses the maximum CTC-AE grade and display n and % for each category (total, SOC, and PT). Again, the number of patients in SAF is used as denominator and each maximum severity is counted only once in the respective category.

All patient data are listed in CSR section 16.2. Additionally **data listings** relevant for safety assessment are presented in section 14.3.2. Here, the patient identification, the verbatim term given by the investigator, MedDRA preferred term and system organ class, start/end dates,

severity, seriousness, relationship to study drug and action taken are listed. The AE onset will also be shown relative (in number of days) to the date of initial dose.

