
2.8.1.1 Adverse events of special interest / grouping of AEs

The following (S)AEs of special interest were defined:

- Neutropenia (MedDRA Code 10029354)
- Hepatobiliary toxicity, defined as grade 3 or 4 increases in ALT or/and AST (MedDRA Codes: 10001551, 10003481)
- QT prolongation (MedDRA Code 10014387)

In addition, the time to occurrence from start of study drug to the (first) onset of a TEAE of special interest (TEAESI) is analysed by sample statistics as well as the duration (start – end + 1 day). Further the number of TAEASI occurring in one patients during on-treatment period is displayed.

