2.11 Patient-reported outcomes

Health-related quality of life (HRQoL) was assessed using the EORTC QLQ-C30 and BR23 questionnaires.

Descriptive statistics was used to summarize the individual item and scored sub-scale scores of QoL data at each scheduled assessment time point. Patients were included if they completed at least one questionnaire item. Additionally, change from baseline in the domain scores at the time of each assessment was summarized. Patients with an evaluable baseline score and at least one evaluable post-baseline score during the treatment period were included in the change from baseline analyses (assessments after disease progression were excluded).

The time (from start of study drug) to 10% deterioration in EORTC QLQ-C30 was analysed by sample statistics.

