5.3 Programming rules

5.3.1 Calculation of ‘time to event’ variables

Time to event = end date - start date + 1 (in days).

When no post-baseline tumor assessments was available, the date of first application of treatment was used as end date (duration = 1 day) when time was to be censored at last tumor assessment, i.e. time to event variables can never be negative.

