5.4.6 AE date imputation

In case of missing or partial start date or end date of an AE, the start date should be shifted to the earliest possible date, but not earlier than the first intake of study drug while the end date should be shifted forward as far as possible.

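### Time to first AESI is summarised without censoring, against the SAP's own Kaplan-Meier rule, and the printed AESI duration formula has its dates reversed

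*SAP*

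**What the plan says.** SAP 1.2 lists time to event, duration and recurrence of AESIs among the endpoints for the secondary safety objective, and the table in SAP 2.8.1 marks those columns for AESIs. The AESIs are neutropenia, grade 3 or 4 ALT/AST increase, and QT prolongation.

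SAP 2.8.1.1 gives the method: time to first onset "is analysed by sample statistics as well as the duration (start – end + 1 day"). It states no censoring date for patients without the event.

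Other parts of the SAP bear on this:

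- SAP 2.1, general rule: "Time-to-event data including rates of affected patients were assessed using the Kaplan-Meier method". Protocol section 10 says the same.
- SAP 5.3.1: "Time to event = end date - start date + 1 (in days").
- SAP 2.4.1, ribociclib interruptions: "The total duration was calculated by end date – start date of interruption", plus 1 day. SAP 5.2.1 likewise takes last minus first administration plus 1 day.
- SAP 2.8.1: adverse event summary tables "include only AEs that started or worsened during the on-treatment period plus 30 days".
- SAP 5.4.6, for missing or partial AE dates: "the end date should be shifted forward as far as possible".

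The length of the observation window follows from Protocol 4.1: "Study treatment will continue until progression, unacceptable toxicity, withdrawal of consent or 80 weeks after the last patient has been enrolled in the trial". The earliest of these applies to each patient. Safety tables are shown by cohort (SAP 2.8).

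**The concern.** Time to first AESI is a censored variable: a patient who stops treatment event-free after a few months tells us only that onset had not occurred by then. Sample statistics drop that information. The resulting median describes onset among those who had the event while observed, and it becomes shorter as the observation window becomes shorter, even when the risk over time is unchanged.

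This matters for comparison. The protocol's own figures suggest much shorter treatment in pretreated than in first-line patients, so cohort B2 could appear to have earlier toxicity simply because it is watched for less time. The same applies between the interim and final analyses, all of which include safety. An events-only median also gives no probability of an event by a stated time.

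For duration, the printed formula subtracts the dates in the wrong order. The end-date rule shifts missing dates forward, and 2.8.1.1 does not say whether an event still unresolved is then treated as having an observed end.

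**Working it through.** The documents give no numerical result on this point, so there is no figure to reproduce.

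**Duration formula.** Let D be the true duration in days, counting both first and last day, so that end − start = D − 1.

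- End − start + 1 = (D − 1) + 1 = D.
- Start − end + 1, as printed, = −(D − 1) + 1 = 2 − D.

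| True duration (days) | As printed |
|---|---|
| 1 | 1 |
| 2 | 0 |
| 3 | −1 |
| 7 | −5 |
| 24 | −22 |

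The 24 days is the median time to resolution of grade 3 or higher ALT/AST elevation on ribociclib plus letrozole reported in Protocol 7.2.2.4.2. The literal formula is right only for one-day events and turns negative from 3 days.

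**Onset.** Inputs from the documents:

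- Median PFS of 25.3 months (first line) and 5.5 months, 95% CI 2.3 to 8.1 (previously treated), Protocol 1.2.6. These serve as proxies for treatment time in cohorts A and B2.
- Median onset of grade 3 or higher ALT and AST elevation of 57 and 62 days, Protocol 7.2.2.4.2.
- Neutropenia onset by Day 15, Protocol 1.2.1.2.1.
- Observation to last dose plus 30 days.

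Assumptions: exponential onset with the same hazard in both cohorts; exponential treatment time, capped at 560 days (80 weeks; earlier enrollees could be followed longer); 30.4375 days per month. True medians of 120 and 182 days are hypothetical, added to show later onset. Each scenario was simulated with 1,000,000 patients.

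| True median onset (days) | Events-only median, A | Events-only median, B2 |
|---|---|---|
| 15 | 14.9 | 14.5 |
| 57 | 53 | 44 (35 to 47 over the PFS interval) |
| 62 | 58 | 47 |
| 120 | 101 | 72 |
| 182 | 135 | 87 |

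The 57-day row can be checked by hand. With onset hazard λ = ln2/57 = 0.01216 and stopping hazard μ, the share of eventual events observed by day 30 is a = 1 − e^(−30λ) = 0.3057. For t > 30 the observed share is a + b(1 − e^(−(λ+μ)(t−30))), where b = e^(−30λ)·λ/(λ+μ). The median is the t at which this reaches half the total observed share.

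- A: μ = ln2/(25.3 × 30.4375) = 0.00090, b = 0.6465, total by day 590 = 0.9517, half = 0.4759. Then t = 30 − ln(1 − (0.4759 − 0.3057)/0.6465)/0.01306 = 53.4 days.
- B2: μ = ln2/(5.5 × 30.4375) = 0.00414, b = 0.5180, total = 0.8236, half = 0.4118. Then t = 30 − ln(1 − (0.4118 − 0.3057)/0.5180)/0.01630 = 44.1 days.

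The closed form agrees with the other A and B2 values in the table to within about a day. Since the hazard is the same in both cohorts, a method that handles the censoring targets the same onset distribution in each.

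QT prolongation was not simulated. Protocol 1.2.1.2.1 describes QT changes as evident in the first cycle, which points to a small effect, as for neutropenia.

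**The case against.** Several points on the other side carry weight.

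**Reversed dates.** SAP 2.4.1, 5.2.1 and 5.3.1 all have the order right, and negative durations would be noticed at once. A reader might infer that the reported durations will come out negative. The documents do not support that: they show a wrong printed formula, not a wrong program.

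**Event-free patients.** With the incidences reported in Protocol 1.2.6, 1 − 0.608 = 39% of patients would have no neutropenia and 1 − 0.102 = 90% no grade 3 or 4 ALT increase. A reader might infer that these patients vanish from the safety analysis. They do not: the incidence table in SAP 2.8.1 uses the whole Safety Set as denominator. Nor do these shares measure any shift in the onset median.

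**Size.** The documents place most events early. Protocol 7.2.2.4.2 has 31 of 37 (83.8%) grade 3/4 ALT/AST increases in the first 6 months. The large gaps in the table come from hypothetical late onsets.

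**Convention.** Protocol 7.2.2.4.2 itself quotes medians among patients with events, so the same summary allows comparison with the reference trial. The specific rule in 2.8.1.1 could also be read as overriding 2.1.

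**End dates.** SAP 5.4.6 concerns missing or partial dates, and Protocol 8.1.1 asks for follow-up until resolution or until an event is judged permanent, which limits missing end dates. The RAP modules, which are not available here, may say more.

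These points justify keeping an events-only summary and reading the formula as a slip. They do not remove the dependence on follow-up between cohorts and interim analyses. The SAP does not label the summary as conditional on an event, whereas the protocol labels the reference figures that way. Crude incidence per period does not give the probability of an event by a given time. Events judged permanent are those for which a forward-shifted end date would mislead most.

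**Conclusion.** The point holds as a minor one. SAP 2.8.1.1 departs from the Kaplan-Meier rule in SAP 2.1 for a named secondary safety endpoint. Its coverage of event patients only is an inference, though a necessary one, because no onset date or censoring rule exists for the others.

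The effect on the onset median is negligible for early neutropenia (14.9 against 14.5 days) and modest for hepatic events (53 against 44 days for the same true median of 57). It would be larger only for onsets later than the documents describe. These sizes rest on exponential times, a common hazard and PFS standing in for treatment time, and should be read as illustration. They do not support a general claim that onset of all three AESIs is materially biased.

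The duration formula is wrong as printed and probably a drafting slip. The handling of unresolved AESIs is unstated in 2.8.1.1. All of this concerns descriptive safety summaries; the CBR analysis is untouched.

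**What to change.** 1. Analyse time to first AESI in the Safety Set by Kaplan-Meier or cumulative incidence, censoring event-free patients at the earlier of last dose plus 30 days or data cut-off. Report event probabilities at fixed times by cohort, since a Kaplan-Meier median will not be reached for an uncommon event.
2. Keep the events-only statistics as a supplement, labelled as conditional on having an event.
3. Correct the AESI duration to end − start + 1 day and confirm that the program matches.
4. Treat AESIs unresolved at cut-off as censored in the duration summary, instead of using forward-imputed end dates as observed.
5. Check SAP 2.11 for the same issue: "The time (from start of study drug) to 10% deterioration in EORTC QLQ-C30 was analysed by sample statistics".

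The cost is a few lines of SAP wording and about one extra table per AESI. No new data are needed.

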2.8.2 Deaths

The number of deaths in the pre-, on- and post-treatment period plus 30 days were displayed as absolute and relative frequencies with 95% confidence intervals. Deaths are listed by patient.

2.8.3 Laboratory data

Normal laboratory values were not documented in the CRF. Abnormal laboratory parameters that induced clinical signs or symptoms, required therapy or required changes in study drug(s) constituted an adverse event and were recorded on the Adverse Events CRF. These relevant laboratory values associated with an adverse event were listed only.

2.8.4 Other safety data

2.8.4.1 ECG and cardiac imaging data

ECG results were summarized using frequency distributions by visit.

2.8.4.2 Vital signs

Vital signs were summarized descriptively by visit for baseline and all post-baseline time points and change from baseline to these time points.

2.8.4.3 ECOG Performance Status

The ECOG Performance Status was summarized using frequency distributions by visit. Shifts from baseline value to worst (i.e. the highest) post-baseline value were summarized using frequency distributions.

2.9 Pharmacokinetic endpoints

Not applicable

2.10 PD and PK/PD analyses

Not applicable

2.11 Patient-reported outcomes

Health-related quality of life (HRQoL) was assessed using the EORTC QLQ-C30 and BR23 questionnaires.

Descriptive statistics was used to summarize the individual item and scored sub-scale scores of QoL data at each scheduled assessment time point. Patients were included if they completed at least one questionnaire item. Additionally, change from baseline in the domain scores at the time of each assessment was summarized. Patients with an evaluable baseline score and at least one evaluable post-baseline score during the treatment period were included in the change from baseline analyses (assessments after disease progression were excluded).

The time (from start of study drug) to 10% deterioration in EORTC QLQ-C30 was analysed by sample statistics.

2.12 Biomarkers

Analysis of Biomarker was described in a stand-alone analysis plan document.

2.13 Other Exploratory analyses

Multivariate regression analysis to identify prognostic factors for Neutropenia respectively AST/ALT increase.

This analysis was not foreseen in the study protocol but included on request of the principal investigator for the presentation of interim and final results.

Two separate multivariate regression analyses were calculated for these interesting events (dependent variables):

1. Neutropenia, selected from AE data set via PTs “neutropenia” and/or “neutrophil count decreased”
2. Increase in ALT or AST: Selected from AE dataset via PTs “ALANINE AMINOTRANSFERASE INCREASED” and/or “ASPARTATE AMINOTRANSFERASE INCREASED”

The following effects (without interactions) were investigated by Type 3 estimates and Wald's confidence intervals for Odds ratios:

- Age at baseline (categorical): <60 years, 60-70 years, and >= 70 years
- BMI at baseline (categorical, rounded to integers): < 20, 20-25, 26-29, and >30 kg/m²
- Presence (no vs. yes) of bone metastases at study start
- Use of chemo therapy as prior antineoplastic medication (no vs. yes)
- Therapy line: 1st, 2nd, and >= 3rd

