1.2.5 Low potential for drug-drug interactions with goserelin

The metabolism of goserelin is not CYP-mediated; rather hydrolysis of C-terminal amino acids is the major clearance mechanism. No formal clinical DDI studies have been conducted or reported with goserelin. Based on the available information, goserelin is not expected to affect the metabolism of nor be affected by co-administered drugs (Zoladex® Prescribing Information).

1.2.6 Summary of available results from patients treated with the combination of ribociclib 600 mg and letrozole 2.5 mg daily

Study CLEE011X2107, is a multicenter phase Ib/II dose escalation/expansion study of LEE011 and BYL719 in combination with letrozole in adult patients with advanced estrogen receptor positive (ER+) breast cancer. Patients must be postmenopausal with metastatic or locally advanced ER+, HER2-negative breast cancer. Dosing in Arm 1 (letrozole 2.5 mg once daily on days 1-28 with LEE011 600 mg once daily on days 1-21 of a 28 day cycle since there is a 7 day rest from LEE011 treatment in each cycle) began on December 3, 2013, and as of October 30, 2015, 47 patients have been treated (dose escalation and dose expansion). 17 of 19 patients (90%) in dose escalation were previously treated for ABC (previously treated group), 27 of 28 patients (96%) in dose expansion were treatment-naïve for ABC (treatment-naïve group).

Treatment has been discontinued in all 19 previously treated pts (100%) due to progression of disease (15 pts [79%]), AEs (2 pts [11%]: Grade 3 alanine aminotransferase increased and Grade 4 myelodysplastic syndrome), and physician decision (2 pts [11%]). Ten pts (36%) in the treatment-naïve group have discontinued treatment due to progression of disease (8 pts [29%]) and physician decision (2 pts [7%]). The median (range) duration of treatment exposure was 16 (9-65) weeks in the previously treated group and 36 (9-74) weeks in the treatment-naïve group; 6 previously treated pts (32%) and 22 treatment-naïve pts (79%) received treatment for ≥6 cycles. Ribociclib dose reductions occurred in 4 previously treated pts (21%; 1 reduction each) and in 4 treatment-naïve pts (14%; 1 reduction each). Ribociclib treatment interruptions due to AEs occurred in 6 previously treated pts (32%) and in 10 treatment-naïve pts (36%).

Table 1-2 Adverse events suspected to be study drug-related (All-Grade ≥15% in all pts)

AE	Previously Treated Group (n=19)		Treatment-naïve Group (n=28)		All Pts (N=47)	

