	C1D21	2.0 (0.7-8.0) [34]	93.4 \pm 36 [34]	1840 \pm 827 [31]	5.2 \pm 2.2 [24]	77.3 \pm 36.6 [24]	1.7 \pm 0.8 [29]

AUC0–24h, area under curve between 0 and 24 hours; C, Cycle; CL/F, apparent oral clearance of drug; Cmax, maximum plasma concentration; D, Day; pts, patients; Racc, accumulation ratio; SD, standard deviation; T1/2, acc, elimination half-life; Tmax, time to reach maximum plasma concentration. *Mean (range) [n]. †Mean \pm SD [n].
Data cut-off: October 30, 2015.

Of the 47 pts evaluable for response per RECIST v1.1, one complete response (CR; treatment-naïve group) was observed. In the previously treated group, 1 pt (5%) had a confirmed partial response (PR), 7 pts (37%) had neither complete response nor progressive disease (NCRNPD; non-measurable disease), 7 pts (37%) had stable disease (SD;

measurable disease), and 4 pts (21%) had progressive disease (PD). A summary of best overall responses for pts in the treatment-naïve group is shown in [Table 1-4](#). As of the October 30, 2015 data cut-off date, the median PFS in the treatment-naïve group had not been reached; pts are being monitored for disease progression.

As of August 19, 2016, 47 patients had been treated with ribociclib 600 mg QD (3-weeks-on/1-week-off) + letrozole 2.5 mg QD (continuous; Table 1). [Table 1-1](#). 17 of 19 patients (89%) in dose escalation were previously treated for aBC (previously treated group). 27 of 28 patients (96%) in dose expansion were treatment-naïve for aBC (first-line group).

Treatment has been discontinued in all 19 patients in the previously treated group (100%) and 15 patients (54%) in the first-line group.

Median progression-free survival (PFS) in the first-line group was 25.3 months; 11 patients had disease progression and 17 patients were censored at the data cut-off date, with 13 patients still ongoing for further PFS follow up.

Two complete responses (CRs) were observed in the first-line group; overall response rate was 46% and clinical benefit rate was 79%.

Median PFS in the previously treated group was 5.5 months (95% confidence interval: 2.3–8.1); 14 patients had disease progression and 5 patients were censored at the data cut-off date, with no patients ongoing for further PFS follow-up. (Munster et al. presented at SABCS, San Antonio, TX, 6–10 December 2016, Abstract P-4-22-18).

Table 1-4 Summary of best overall response for the treatment-naïve group per investigator assessment

	Treatment-naïve Group	

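### The exploratory ALT/AST model ignores time at risk, so its therapy-line odds ratio is pulled down by the shorter treatment of pretreated patients

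*SAP*

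**What the plan says.** SAP 2.13 describes its aim as "Multivariate regression analysis to identify prognostic factors for Neutropenia respectively AST/ALT increase". Two models are fitted. The outcomes are taken from the adverse event data by preferred term: "Neutropenia, selected from AE data set via PTs" and, for the liver, "Increase in ALT or AST: Selected from AE dataset via PTs". Neither definition carries a grade limit or a time window.

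On method, the section says "The following effects (without interactions) were investigated by Type 3 estimates and Wald's confidence intervals for Odds ratios". The word logistic does not appear, but odds ratios with Type 3 tests for an event that is present or absent describe that model. The five factors are age, BMI, bone metastases, prior chemotherapy and "Therapy line: 1st, 2nd, and >= 3rd". There is no exposure covariate, offset or censoring rule, and no analysis set is named. The section states that the analysis is not in the protocol and is meant for presenting interim and final results.

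Protocol 1.2.6 gives the phase Ib experience with the same combination. Median exposure was "16 (9-65) weeks in the previously treated group and 36 (9-74) weeks in the treatment-naïve group". Six cycles or more were reached by 6 of 19 and 22 of 28 patients. "Median PFS in the previously treated group was 5.5 months", against 25.3 months in first line.

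**The concern.** The outcome is whether an event was ever recorded over whatever time each patient was treated. Equal odds of that outcome mean equal risk on treatment only if time on treatment is unrelated to the factor tested. For therapy line, the protocol's own figures show a strong relation.

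Patients who stop sooner have less time in which a first ALT/AST rise can be seen, so the therapy-line odds ratio mixes liver risk with duration of treatment. The mixing runs one way: later lines look safer than they are per unit of time on drug. Pretreated patients are a main part of the population that this trial adds to the earlier phase III trial. Protocol 1.2.6 lists hepatobiliary toxicity as an important identified risk, and SAP 2.8.1.1 makes it an event of special interest. A reader of the presented odds ratios could take a value near or below 1 as reassurance about later-line patients.

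**Working it through.** SAP 2.13 states no sample size, event count or effect, so there is no plan figure to reproduce. The protocol inputs agree with their own counts: 6/19 = 32%, 22/28 = 79%, 31/37 = 83.8%, 240/334 = 71.9%.

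**Inputs**
- Stopping times (protocol 1.2.6): median exposure 16 against 36 weeks, or 32% against 79% still treated at 24 weeks. The shortest exposure was 9 weeks in both groups.
- ALT/AST onset (protocol 7.2.2.4.2, earlier phase III trial, grade 3/4): medians 57 and 62 days, about 8.5 weeks; 83.8% within 6 months (26 weeks).
- Total incidence: 37/334 = 11.1%, treating the 37 events as patients, or 20% (assumed).
- Phase III exposure used to calibrate the hazard: 71.9% treated for at least 9 months.
- Follow-up cap: 80 weeks.

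**Method.** The probability of a recorded event is p = ∫ h(t)·exp(−H(t))·S(t) dt from 0 to 80 weeks. Here h is the event hazard, constant within 0–8.5, 8.5–26 and over 26 weeks; H is its integral; and S is the share still on drug, with S = 1 to week 9 and exp(−λ(t−9)) after. The odds ratio is [p1/(1−p1)] / [p0/(1−p0)], pretreated over first line. A true hazard ratio (HR) multiplies h in pretreated patients.

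**One case in full (11.1%, median exposures).** λ = ln2/7 = 0.099 per week for pretreated and ln2/27 = 0.026 for first line. Calibration gives h of about 0.0070, 0.0027 and 0.0006 per week.
- HR 1: p1 = 0.0802, p0 = 0.1027. Odds 0.0872 and 0.1145; odds ratio 0.76.
- HR 1.5: p1 = 0.1178. Odds 0.1335; odds ratio 0.1335/0.1145 = 1.17. With equal exposure it would be 1.54.

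**Range over the exposure and incidence inputs, ALT/AST**

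| True HR | Odds ratio as planned | Odds ratio at equal exposure |
|---|---|---|
| 1 | 0.66–0.79 | 1.00 |
| 1.5 | 1.02–1.21 | 1.54–1.59 |
| 2 | 1.42–1.67 | 2.11–2.24 |

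Counting events to 30 days after last dose, or using PFS-based stopping times instead, gives about 0.70–0.81 at HR 1 and 1.10–1.25 at HR 1.5. Pairing 32% at 24 weeks with the 36-week median, which makes the gap smallest, and adding the 30 days goes slightly further. At HR 1: p = 0.0922 and 0.1072, odds 0.1016/0.1201 = 0.85. At HR 1.5: p1 = 0.1350, odds 0.1561/0.1201 = 1.30. Dropping the 9-week minimum goes the other way: 0.57–0.73 and 0.88–1.12.

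**Neutropenia (70% incidence, 9-week minimum).** At HR 1 the odds ratio is 0.94–0.96 with a median onset of 2 weeks and 0.79–0.86 with 4 weeks. At HR 1.5 it is 1.57–2.05, against 2.08–2.15 at equal exposure, so the excess stays visible. Only if stopping starts on day 1 does it fall to 1.05–1.53.

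**Does allowing for time at risk repair it?** In 1,000 simulated trials per setting (an assumed 100 pretreated of 500, two groups, no other covariates), a model using time at risk returned median HRs of 0.98–1.00, 1.47–1.51 and 1.97–2.00 for true values of 1, 1.5 and 2. A significant excess was found in 23–39% of trials at HR 1.5 and 62–85% at HR 2, against 6–8% and 28–41% with the odds ratio. A logistic model limited to the first 9 weeks also works: odds ratios 1.00, 1.52–1.54 and 2.06–2.12.

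**The case against.** The probability of an event over the whole treatment course is a legitimate quantity, and the odds ratio describes it without bias. This stands. The difficulty is that SAP 2.13 names no such target, and the language of prognostic factors invites a reading as risk on drug.

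The exposure figures come from 47 patients. The naïve group was still partly on treatment at the cut-off, which understates the gap. The onset timing is for grade 3/4 events while the model counts any grade; timing for all grades is not in the documents. The number of pretreated patients is not given either. These points limit precision but not direction.

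Exposure and AESI onset times are tabulated by cohort, so readers can see the difference in treatment time, but the regression does not use it.

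Several stronger readings are tempting and unsupported:
- That both models are seriously distorted. Protocol 1.2.1.2.1 places neutropenia onset by Day 15, before exposure diverges.
- That a real liver excess in pretreated patients is being hidden. No passage suggests one, and the HRs of 1.5 and 2 are hypothetical. The phase Ib ALT counts, 1/19 against 6/28, fit the pattern (odds ratio 0.20) but have Fisher p = 0.22.
- That median PFS can stand for time on drug. It makes the gap 4.6-fold (25.3/5.5) against 2.25-fold (36/16) for exposure, and treatment may continue beyond radiologic progression (protocol 7.2.1.1).
- That SAP 2.1 already requires time-to-event methods here. Its sentence, "Time-to-event data including rates of affected patients were assessed using the Kaplan-Meier method", is a general statement, and SAP 2.8.1 plans adverse event incidence as simple proportions.

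**Conclusion.** The point holds for ALT/AST and for the therapy-line factor. With equal hazard on drug, the planned odds ratio for pretreated against first-line patients would be about 0.66 to 0.81, a false suggestion of protection. A 1.5-fold excess would show as about 1.0 to 1.25 and could easily be missed. A twofold excess would be attenuated but visible.

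This rests on three assumptions: exposure in this trial differs by line roughly as in phase Ib, any-grade ALT/AST onset resembles the grade 3/4 timing, and few patients stop in the first 9 weeks. At the interim analyses, staggered entry adds further variation in follow-up.

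For neutropenia the effect is small to moderate and a real excess would remain visible. The odds ratios are not invalid; they answer a cruder question than the section's aim suggests. The consequence is confined to an exploratory analysis outside the protocol, with no bearing on the primary endpoint.

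**What to change.** In SAP 2.13, add for ALT/AST, and for consistency neutropenia, a Cox cause-specific hazard model for time from first dose to first treatment-emergent event. Use the Safety Set and the same five factors. Censor at the earliest of last study dose plus 30 days, death, or data cut-off. Report hazard ratios with 95% confidence intervals and base the therapy-line interpretation on them. A logistic model for events in a fixed early window, for example 9 weeks, is an acceptable alternative.

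Keep the existing odds ratios, which may already have been shown at interim presentations, and label them as crude risk over the whole treatment course, not adjusted for time at risk.

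The cost is one extra model per event and a check of proportional hazards. AE onset relative to first dose (SAP 2.8.1) and first and last dose dates (SAP 5.2.1) are already available. Time to onset is already derived for the events of special interest, though the liver event there is limited to grade 3/4, so that derivation must be extended to any grade.
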